6.3. Subset Analyses

There are no planned subset analyses.

6.4. Baseline and Other Summaries and Analyses

6.4.1. Demographic Summaries

Demographic characteristics (age, gender, ethnicity, race, weight, height and body mass index) will be summarized for enrolled population in accordance with the CaPS.

6.4.2. Study Conduct and Participant Disposition

Participants evaluation groups will show end of study participant disposition. Frequency counts will be supplied for participant discontinuation(s) by treatment. Data will be reported in accordance with the CaPS.

6.4.3. Study Treatment Exposure

Study treatment exposure will be listed.

6.4.4. Concomitant Medications and Nondrug Treatments

All concomitant medication(s) as well as non-drug treatment(s) will be reported in the listings.

CCI
[REDACTED]
[REDACTED]
[REDACTED]

6.5.1. Adverse Events

Adverse events will be reported in accordance with the CaPS.

Participant discontinuations due to adverse events will be detailed by treatment. Data will be reported in accordance with the CaPS.

6.5.2. Laboratory Data

Laboratory data will be listed and summarized by treatment in accordance with the CaPS.

6.5.3. Vital Signs

Vital sign data will be databased and available upon request.

6.5.4. Electrocardiograms

ECG data will be databased and available upon request.

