Visit Identifier Abbreviations used in this table may be found in Section 10.10	Screen	Periods 1, 2 and 3									F/U	Early Term Discont	Notes
		Day -1	Day 1	Day 2	Day 3	Day 4	Day 5	Day 6	Day 7	Day 8			
											28-35 days		
 • All screening should be done \leq 28 days before the first dose. • Day relative to start of study intervention (Day 1). • At least a 16 day washout interval between Day 1 in each subsequent period. • Follow-up may occur via telephone contact and must occur 28 to 35 days after administration of the final dose of study intervention.
COVID-19 testing	X	X				X							
 • The testing for COVID-19 pathogen will be performed at each visit per local site procedures. For participants admitted for residence, a subsequent COVID-19 test will be performed after 4 days (ie, upon completion of 4 x 24 hours in house), or if they develop COVID-19 like symptoms.
COVID-19 check temperature	X	X	X	X	X	X	X	X	X				
 • To be done at least daily during residence.
Study intervention administration			X										
 • Participants fasted overnight (minimum of 10 hours) prior to dosing and for 4 hours postdose on Day 1 (Periods 1 and 2 only).
Pharmacokinetic blood sampling			X	X	X	X	X	X	X	X	X		
 • Final visit procedures will be performed on the last day of the last period (Day 8 Period 3), or upon study discontinuation.

PFIZER CONFIDENTIAL

Table 1. Study Schedule of Assessment

Visit Identifier Abbreviations used in this table may be found in Section 10.10	Screen	Periods 1, 2 and 3									F/U	Early Term Discont	Notes
		Day -1	Day 1	Day 2	Day 3	Day 4	Day 5	Day 6	Day 7	Day 8			
CCI													
Serious and non-serious AE monitoring		X	X	X	X	X	X	X	X	X	X		• See Section 8.4.3 for follow-up AE and SAE assessments.
Prior/concomitant medication and treatments		X	X	X	X	X	X	X	X	X	X		
CRU discharge										X			

PFIZER CONFIDENTIAL

Pharmacokinetic Sampling Schema

Visit Identifier	Periods 1-3													Notes				
Study Day	1				2	3	4	5	6	7	8	Early Term/ Discont						
Hours Before/After Dose	0	0.5	1	2	3	4	6	8	12	24	48	72	96	120	144	168		Hour 0 = predose sample collection
Study intervention administration	X																	
PK blood sampling	X	X	X	X	X	X	X	X	X	X	X	X	X	X	X	X	X	

PFIZER CONFIDENTIAL

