6.1. Study Intervention(s) Administered

Eligible participants who continue to meet entry criteria will be admitted to the CRU on Day -1 and will be required to stay in the CRU for 8 overnight stays in each period. All participants will be discharged from the CRU following completion of the discharge evaluation, which includes adverse event monitoring, physical examination (at investigator discretion), vital signs, ECG measurements, and safety laboratory tests.

Study Intervention(s)			
Intervention Name	Tafamidis free acid tablet (fasted)	Tafamidis meglumine soft gelatin capsule (fasted)	Tafamidis free acid tablet (fed)
Arm Name (group of participants receiving a specific treatment or no treatment)	Treatment A	Treatment B	Treatment C
Type	Drug	Drug	Drug
Dose Formulation	Tablets	Softgel capsules	Tablets
Unit Dose Strength(s)	12.2 mg	20 mg	12.2 mg
Dosage Level(s)	1 x tablet	1 x capsule	1 x tablet
Route of Administration	Oral	Oral	Oral
Use	Experimental	Experimental	Experimental
IMP or NIMP/AxMP	IMP	IMP	IMP
Sourcing	Provided centrally by the sponsor Refer to the IPM	Provided centrally by the sponsor Refer to the IPM	Provided centrally by the sponsor Refer to the IPM
Packaging and Labeling	Study intervention will be provided in bottles. Each bottle will be labeled as required per country requirement. The product will be provided as open supplies.	Study intervention will be provided in bottles. Each bottle will be labeled as required per country requirement. The product will be provided as open supplies.	Study intervention will be provided in bottles. Each bottle will be labeled as required per country requirement. The product will be provided as open supplies.
Current/Former Name(s) or Alias(es)	PF-06291826	PF-06291826 / Vyndaqel®	PF-06291826

Study Arm(s)			
Arm Title	Treatment A	Treatment B	Treatment C
Arm Type	Test - fasted	Reference - fasted	Test - fed
Arm Description	Participants will receive a single 12.2 mg	Participants will receive a single commercial 20	Participants will receive a single 12.2 mg

Study Arm(s)			
	tafamidis free acid tablet, fasted	mg tafamidis meglumine capsule	tafamidis free acid tablet, fed
Associated Intervention Labels	Tafamidis 12.2 mg tablets	Tafamidis meglumine 20 mg capsules	Tafamidis 12.2 mg tablets

Study interventions will be supplied by Pfizer as tafamidis 12.2 mg tablets and tafamidis meglumine 20 mg soft gelatin capsules.

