9.3.2. Safety Analyses

All safety analyses will be performed on the safety population.

AEs, ECGs, BP, pulse rate, and safety laboratory data will be reviewed and summarized on an ongoing basis during the study to evaluate the safety of participants. Any clinical laboratory, ECG, BP, and pulse rate abnormalities of potential clinical concern will be described. Safety data will be presented in tabular and/or graphical format and summarized descriptively, where appropriate.

Medical history and physical examination and neurological examination information, as applicable, collected during the course of the study, will be considered source data and will not be required to be reported, unless otherwise noted. However, any untoward findings identified on physical and/or neurological examinations conducted during the active collection period will be captured as AEs, if those findings meet the definition of an AE. Data collected at screening that are used for inclusion/exclusion criteria, such as laboratory data, ECGs, and vital signs, will be considered source data, and will not be required to be reported, unless otherwise noted. Demographic data collected at screening will be reported.

CCI

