3.5. Safety Endpoints

The following data are considered in standard safety summaries (see protocol for collection days, baseline assessment, and list of parameters):

- adverse events (AE)

PFIZER CONFIDENTIAL

- laboratory data
- vital signs data
- ECG results

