5.3.2. Safety Data

Missing values in standard summaries of AEs, laboratory data, vital signs, and ECGs will be imputed according to CaPS.

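### SAP 6.5.3 and 6.5.4 plan no output for vital signs or ECGs, which departs from the protocol's commitment to describe abnormalities, and SAP 2.1 does not declare the change

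*SAP*

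**What the plan says.** The protocol makes two statements in the Safety Analyses part of Section 9.3.2. (The number 9.3.2 is used twice; the other one covers PK methods.) The first has no qualifier: "Any clinical laboratory, ECG, BP, and pulse rate abnormalities of potential clinical concern will be described". The second is softer: "Safety data will be presented in tabular and/or graphical format and summarized descriptively, where appropriate".

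The SAP points two ways:

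- SAP 3.5 introduces a list that includes vital signs and ECG results with the words "The following data are considered in standard safety summaries".
- SAP 5.3.2 gives a missing-data rule for those outputs: "Missing values in standard summaries of AEs, laboratory data, vital signs, and ECGs will be imputed according to CaPS".
- SAP 6.5.3 then says: "Vital sign data will be databased and available upon request".
- SAP 6.5.4 says: "ECG data will be databased and available upon request".

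SAP 6.5.2, between the adverse-event and vital-sign sections, has laboratory data both listed and summarized by treatment. SAP 2.1, the section for changes to the protocol's analysis plan, reports none.

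**The concern.** A commitment to describe abnormalities is not met by keeping the data in a database. The SAP sets out the planned summaries and analyses, and its visible text names no table, listing, narrative or criterion for blood pressure, pulse rate or ECG. A programmer working from Section 6.5 would produce nothing for these data. One working from SAP 3.5 and 5.3.2 would expect to produce standard summaries.

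What is at stake is the safety part of the report. An abnormal value reaches the report as an adverse event only if it was recorded as one. For the rest, a reader could not tell whether no abnormal values occurred or whether none were shown. The pharmacokinetic endpoints play no part in this.

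**Working it through.** No arithmetic applies, and the plan gives no figure to reproduce. The check sets the passages side by side.

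1. **Is the protocol commitment firm?** In Protocol 9.3.2 (Safety Analyses) the words that leave room for judgement belong to the sentence on tabular or graphical presentation. The sentence on describing abnormalities has no such words. The firm commitment is therefore to describe abnormalities, not to produce full summary tables.

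2. **Does the SAP carry it out?** Compare the three kinds of measured safety data that the protocol sentence covers:

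| Data | Protocol 9.3.2, Safety Analyses | SAP 3.5 and 5.3.2 | SAP 6.5 |
|---|---|---|---|
| Laboratory | abnormalities described | in standard summaries | listed and summarized by treatment (6.5.2) |
| Blood pressure, pulse rate | abnormalities described | in standard summaries | database only (6.5.3) |
| ECG | abnormalities described | in standard summaries | database only (6.5.4) |

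The first row agrees across the documents. The other two do not. SAP 3.5.3 and 3.5.4 also define baselines, and 3.5.4 a QTcF formula, that no visible output uses.

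3. **Is the departure allowed?** Yes. Protocol Section 9 lets the SAP modify the outlined analyses and ties a protocol amendment to major changes in the primary endpoint definitions or their analyses. Vital signs and ECGs are not primary endpoints.

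4. **Is the departure declared?** No. SAP 2.1 reports no modification.

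5. **What would go unreported?** Protocol 7.1.1 sends new clinically relevant ECG findings to adverse-event reporting. Protocol 10.3.1 does the same for ECG and vital-sign results that the investigator considers clinically significant. SAP 6.5.1 reports adverse events. What remains is abnormal blood pressure, pulse rate and ECG values that were not recorded as adverse events, chiefly those the investigator did not judge clinically relevant or significant.

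6. **How sure can one be?** Text is blacked out in three relevant places: the safety assessments in Protocol 8.3, the end of the Safety Analyses text in Protocol 9.3.2, and a block just before SAP 6.5.1. Any of these could hold criteria or a general statement on safety outputs. SAP 6.5.3 and 6.5.4 are themselves visible and specific.

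**The case against.** The strongest reply has three parts.

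First, the SAP is the more detailed document and is expressly allowed to modify the protocol. Within it, Section 6 is where outputs are specified. SAP 3.5 and 5.3.2 can be read as general conventions that promise no particular vital-sign or ECG table. This largely stands. It means the database-only rule may well be deliberate and permitted. It does not explain why SAP 2.1 reports no modification.

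Second, adverse-event reporting already does most of the work for ECGs. Protocol Appendix 8 is the only visible account of ECG findings of potential clinical concern, and it sorts them by whether they may or do qualify as adverse events. The protocol asks for description, which a narrative could supply without a listing. This stands in part. Reporting through adverse events depends on investigator judgement, and Appendix 8 says of many findings only that they may qualify. The protocol sentence covers abnormalities of potential concern whether or not they were recorded as events. No narrative is planned in the visible SAP.

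Third, the redactions may hide the missing wording. This stands as a limit on confidence.

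A reader might go further and infer that ECG and vital-sign safety findings will be suppressed, or that the protocol has been breached and needs amending. The documents support neither. Findings judged clinically relevant or significant still reach the report as adverse events, and Protocol Section 9 permits the change without an amendment.

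**Conclusion.** The point holds as an undeclared departure in descriptive safety reporting. The protocol commits to describing these abnormalities. The visible part of SAP 6.5 provides no means of doing so for vital signs and ECGs, other parts of the SAP presuppose summaries of them, and SAP 2.1 says nothing has changed.

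Severity is minor. The gap is limited to values not recorded as adverse events. Their number cannot be estimated from the documents, and a count of planned assessments would not measure it. The bioequivalence and food-effect conclusions are unaffected.

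Confidence is moderate. The conclusion assumes that the redacted passages contain no statement that already provides for these outputs, and that SAP 6.5.3 and 6.5.4 would be followed as written.

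**What to change.** Choose one of two routes.

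**Restore the reporting.** In SAP 6.5.3 and 6.5.4, replace the database-only sentences with a listing, by treatment received, of blood pressure, pulse rate and ECG values of potential clinical concern. The SAP should name the criteria. SAP 3.5.2 refers to the sponsor's reporting standards for laboratory tests only, so it should not be assumed to cover these data. If the ECG interval items in Protocol Appendix 8 are used, keep their wording in full. The items on PR interval above 280 ms and QTcF above 480 ms apply to *new* prolongation, so a post-dose value alone does not decide them. Judge them against the Day 1 Period 1 baseline already defined in SAP 3.5.4.

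**Or declare the omission.** If database-only handling is intended, say so in SAP 2.1 and bring SAP 3.5 and 5.3.2 into line.

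The first route costs one or two extra listings and needs no new data collection: the protocol already plans a "discharge evaluation, which includes adverse event monitoring, physical examination (at investigator discretion), vital signs, ECG measurements, and safety laboratory tests". The second costs a sentence in SAP 2.1 and two small edits. Under Protocol Section 9 neither route needs a protocol amendment.

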7. INTERIM ANALYSES

No formal interim analysis will be conducted for this study. As this is an open-label study, the sponsor may conduct unblinded reviews of the data during the course of the study for the purpose of safety assessment, facilitating PK modeling, and/or supporting clinical development.

Final analysis will follow the official database release. As this will be an open-label study, there is no formal unblinding of the randomization code.

APPENDICES

Appendix 1. SAS Code for Analyses

An example of the PROC MIXED code is provided below:

For primary objective: Treatment A (Test) vs Treatment B (Reference)

```
proc mixed data=tab.pk;
  where trt in ("A", "B");
    class seq period trt participant;
    model l&var=seq period trt/ ddfm=KR;
    random participant(seq) /participant=participant(seq);
    lsmeans trt;
    estimate 'A vs B' trt 1 -1 /cl alpha=0.1;

    ods 'Estimates' out=est&var;
    ods 'lsmeans' out=ls&var;
    ods 'covparms' out=cov&var;
    ods 'tests3' out=tst&var;
run;

/* Letter assignments for treatments (trt) within the estimate statement above are as follows
A: 12.2 mg tafamidis free acid tablet, fasted (Test)
B: Commercial 20 mg tafamidis meglumine soft gelatin capsule, fasted (Reference) */
```

For secondary objective: Treatment C (Test) vs Treatment A (Reference)

```
proc mixed data=tab.pk;
  where trt in ("A", "C");
    class trt participant;
    model l&var=trt / ddfm=KR;
    random participant / subject=participant;
    lsmeans trt;
    estimate 'C vs A' trt -1 1 /cl alpha=0.1;

    ods 'Estimates' out=est&var;
    ods 'lsmeans' out=ls&var;
    ods 'covparms' out=cov&var;
    ods 'tests3' out=tst&var;
run;

/* Letter assignments for treatments (trt) within the estimate statement above are as follows;
A: 12.2 mg tafamidis free acid tablet, fasted (Reference)
C: 12.2 mg tafamidis free acid tablet, fed (Test) */
```

Appendix 2. List of Abbreviations

Abbreviation	Term
%CV	coefficient of variation
AE	adverse event
CCI	
AUC _{inf}	area under the concentration-time curve from time 0 to infinity
AUC _{last}	area under the concentration-time curve from 0 to time of last measurable concentration
AUMC _{inf}	area under the first moment curve from zero time to infinity
BLQ	below the limit of quantitation
BP	blood pressure
CaPS	Clinical Data Interchange Standards Consortium and Pfizer Standards
CI	confidence interval
C _{last}	estimated plasma concentration at the last quantifiable time point estimated from the log-linear regression analysis
C _{max}	maximum observed plasma concentration
CSR	clinical study report
ECG	electrocardiogram
HR	heart rate
k _{el}	the terminal phase rate constant calculated by a linear regression of the loglinear concentration-time curve
LLQ	lower limit of quantitation
mg	milligram
m _R	the average bioavailability on a log scale for the Reference product
CCI	
m _T	the average bioavailability on a log scale for the Test product
N/A	not applicable
NC	not calculated
ND	not done
NS	no sample
PK	pharmacokinetic(s)
PR	pulse rate
q _L	lower limit of bioequivalence
QRS	Combination of Q-, R- and S- wave on an electrocardiogram representing ventricular depolarization
QTc	corrected QT
QTcF	corrected QT (Fridericia method)
q _U	upper limit of bioequivalence
RR	respiratory rate
SAP	statistical analysis plan
SD	standard deviation
SoA	schedule of activities

Abbreviation	Term
cc	[REDACTED]
TEAE	treatment emergent adverse event
t_{last}	time of last measurable concentration
CCI	[REDACTED]
